3.2 Sample size estimation

It is planned to complete 18 subjects in Part A and 60 subjects in Part B in this study. This sample size is chosen on clinical rather than statistical rationale. No formal sample size calculations were performed. The sample size is considered adequate to address the study goals.

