----------------------	---

	
Patients will need to daily record the itch condition in the patient diary by themselves including the daily 24-hour worst itch NRS, application time/ site of the study drug, time and intensity of the itch between the morning and evening dose and return the diary at every visit. Patient need to return the study drug and the actual dosing in each patient will be determined by subtract the weight of each returned study drug subtract from the initial weight (T_0).
 
Clinical laboratory tests will be obtained at Day 1, 15, 29. Blood sample for pharmacokinetics will be collected at pre-dose, 48, 120, 168, 336, 504, and 672 hrs post dosing. Subjects will return for a follow-up visit to complete safety evaluations for approximately 35 days after study drug administration.
 
Interim analysis and DSMB:
 
After Part A completion, the interim analysis will plan to be done. DSMB will review interim analysis and give comments on safety or any medical concern to determine whether the study continued or not. Also, DSMB will give comments for LT5001 drug product daily dose and regimen.
 
Part B:
 
This part of study will recruit 90 hemodialysis patients (LT5001: Placebo=1:1) with moderate to severe pruritus. The study will assess safety, and efficacy of LT5001 drug product when applied to skin for 8 weeks with uremic pruritus.
 
Eligible patients will be randomized into LT5001 drug product and placebo treatment groups with 1:1 ratio. [REDACTED] The daily dose and recommended regimen may be adjusted based on DSMB recommendation.
 
Patients will need to daily record the itch condition in the patient diary by themselves including the daily 24-hour worst itch NRS, application site of the study drug, time and intensity of the itch between the morning and evening dose and return the diary at every visit. They will visit at Day 1, 8, 15, 22, 29, 36, 43, 50, and 57 after drug administration.
 
If a subject is withdrawn from the treatment period of the study for reasons not associated with safety considerations, additional subjects may be enrolled if additional data are necessary to establish safety and tolerability.

Estimated Study Duration:	
Part A:
 
Approximately 6 weeks, includes 1 weeks of screening (Diary Run-in), 4 weeks of treatment and 1 week follow up.
 
Part B:

	Approximately 9 weeks, includes 1 weeks of screening (Diary Run-in), 8 weeks of treatment.

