Blood Sampling Schedule	
Pharmacokinetic Assessments
 
Blood Pharmacokinetic Assessments
 
[REDACTED]
 
[REDACTED]
 
[REDACTED]
 
[REDACTED]
 
[REDACTED] . [REDACTED]
 
[REDACTED]
 
[REDACTED]
 
 • Pre-dose, 48, 120, 168, 336, 504, and 672 hrs post dosing
Safety Assessments:	The safety and tolerability of LT5001 drug product will be assessed via the following: 
 • Adverse events • Vital signs (temperature, respiratory rate, systolic and diastolic blood pressure, and pulse rate) • Clinical laboratory tests • Physical examination • Application site examination (dermatitis, pruritus, paresthesia, erythema, dryness, vesicles, irritation, papules, burning)
Test Drug	LT5001 drug product

[figure not shown]
Drug Administration	
Topical administration
 
The study medication will be applied directly to the itching area as instructed by the study staff.
 
Avoid apply LT5001 drug product around the eyes, mouth, nose, mucous membrane, genital, anal region, vascular access for hemodialysis and its surrounding region (1 cm in both sides). Do not apply the study medication on to the vesicles, open wound, or on the area of erythema, rash, swelling, paresthesia, pain, desquamation, discoloration.

Sample Size:	
Part A: Approximately 20 subjects will be screened to achieve 18 subjects enrolled (LT5001: Placebo=12:6).
 
Part B: Approximately 100 subjects will be screened to achieve 90 subjects enrolled (LT5001: Placebo=45:45).

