In the first 7 days of study treatment, patient will also need undergo a 7-day repeated open application tests (ROAT). A 0.5 fingertip unit of the study drug is recommended to apply to a 5x5 cm² fixed pre-marked zone without any skin lesions near the antecubital fossa twice daily in the morning and evening for 7 days. If skin lesion is occurred in the antecubital fossa, it is acceptable to choose the volar forearm or ventral inner arm without skin lesion under the judgment of investigator to perform ROAT (avoid the area depicted in the [Section 7.2 Treatments Administered](#)). Patients will need to daily assess the itch condition at a fixed period by themselves and record in the patient diary including the daily 24-hour worst itch NRS,

application time/ site of the study drug, time and intensity of the itch between the morning and evening dose and return the diary at every visit.

Patients will visit the CRU for dosing on Day 1, and for procedures including clinical laboratory test samplings, physical examinations, vital sign assessments, itch assessment (Skindex-10 and 5D-itch scale), and application site assessments by ICDRG scale (dermatitis, pruritus, paresthesia, erythema, dryness, vesicles, irritation, papules, burning) according to [Table 8.2](#), and PK blood samples will be performed according to Table 2.3. Application site evaluation will be conducted in each visit (Visit 2 to 8) in Part A. Photographs of the application site may be considered under the investigator's judgment (optional). Baseline skin condition performed at screening will be used as reference for comparison.

Patient will need to return the study drug during 3 times per week following his/her dialysis schedule. The actual dosing in each patient will be determined by subtract the weight of each returned study drug from the initial weight (T_0).

Patients will return for a follow-up visit to complete safety evaluations according to [Table 2.1](#). Application site assessments (dermatitis, pruritus, paresthesia, erythema, dryness, vesicles, irritation, papules, burning) by ICDRG scale according to Table 8.2, AEs, and concomitant medications and procedures will be recorded.

Part B:

Part B will be randomized, double-blind, and placebo-controlled. It will enroll 90 patients between 20 to 75 years of age, inclusive.

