10.1 Sample Size Calculation

It is planned to complete 18 subjects in Part A and 90 subjects in Part B in this study. This sample size is chosen on clinical rather than statistical rationale. No formal sample size calculations were performed. The sample size is considered adequate to address the study goals.

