1.1 Preface

The objective of this document is to detail the statistical methodology to be used for the part A and part B statistical analysis of study LT5001-101.

The statistical analysis plan is based on the following information and documents:

- LT5001-101 Protocol V4.0/ Date: 16 Mar 2020
- LT5001-101 Subject Case Report Forms V3.0/ Date: 20 Mar 2020

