3.1 General description

Indication	Hemodialysis patients with moderate-to-severe pruritus
Design	This is a randomized, double-blind, placebo-controlled study containing two parts: part A will assess the safety, tolerability and PK with 4-week treatment, part B will assess safety and efficacy for 8-week treatment. Both parts will apply investigational drug in hemodialysis patients with moderate to severe of uremic pruritus.
Phase	1 (Part A) and 2 (Part B)
Study Site:	[REDACTED] [REDACTED]
Sample size	
Part A:
 
Approximately 20 subjects will be screened to achieve 18 subjects enrolled (LT5001 drug product: Placebo=12:6).
 
Part B:
 
Approximately 66 subjects will be screened to achieve 60 subjects enrolled (LT5001 drug product: Placebo=30:30).

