3.3 Randomisation, blinding and unblinding procedures

Subjects will be randomized into the study once they have completed screening and the Day -1 pre-dosing assessments and have satisfied all eligibility criteria.

Hemodialysis subjects with moderate-to-severe pruritus will be assigned random allocation number as the following ratio in each study part.

For Part A, patients will be randomized into a 2:1 ratio to receive LT5001 drug product or placebo. Thus, LT5001 group, the resulting allocated subjects will be 12 subjects. The placebo group will contain 6 subjects.

For Part B, patients will be randomized into a 1:1 ratio to receive LT5001 drug product or placebo. Thus, LT5001 group, the resulting allocated subjects will be 30 subjects. The placebo group will contain 30 subjects.

QMS Document Name: Statistical Analysis Plan	Page 9 of 33
QMS No (include version ref): STF-015-GL.02	Document date: 09JUL2019
CONFIDENTIAL	

The CRO will maintain the randomization code in a secure location with controls to prevent unauthorized access, including the computer program written to generate the randomization, randomization codes, program log, seed number used by the program, copy of the randomization plan along with approval documentation as appropriate, and the write protected electronic storage medium.

The site and CRO will name an unblinded statistician to provide the randomization code. Investigators, pharmacists, site staff, patients, CRO, and the Sponsor will remain blinded to individual patients' treatment assignment for the duration of the study until the study unblinding has been authorized.

In order to preserve the blind, study drug will be prepared and administered in a manner that masks the content for both the patient and staff member administering the drug.

4 Analysis Sets

Enrolled Population (ENR)

The enrolled population will include all patients who provided informed consent. Summary of screening failures and randomized patients will be displayed for ENR population.

Safety Analysis Set (SAS)

The SAS will include all patients who receive at least 1 dose of LT5001 drug product or placebo in Parts A and B. Patients will be analyzed according to the treatment they actually received.

The Safety Population will be used for all safety analysis (adverse events, clinical laboratory tests, vital signs, physical examinations and application site examination).

Full Analysis Set (FAS)

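### Part B is planned at 90 patients (45:45) in the protocol and at 60 (30:30) in the SAP, and the text does not show which number is in force

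*SAP*

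**What the plan says.** The protocol gives 90 for Part B throughout. The synopsis says "This part of study will recruit 90 hemodialysis patients (LT5001: Placebo=1:1) with moderate to severe pruritus", and its sample size entry adds 45 per arm from about 100 screened. Section 5.1 says of Part B "It will enroll 90 patients between 20 to 75 years of age, inclusive". Section 10.1 says "It is planned to complete 18 subjects in Part A and 90 subjects in Part B in this study".

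The SAP gives 60 throughout. Section 3.1 has 60 enrolled, 30 per arm, from about 66 screened. Section 3.2 says "It is planned to complete 18 subjects in Part A and 60 subjects in Part B in this study". Section 3.3, on randomisation, says "LT5001 group, the resulting allocated subjects will be 30 subjects. The placebo group will contain 30 subjects".

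Part A is 18 (12:6) in both documents, and Part B allocation is 1:1 in both. Both say that the size was chosen on clinical grounds and that no formal calculation was done.

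On versions, SAP 1.1 bases the plan on "LT5001-101 Protocol V4.0/ Date: 16 Mar 2020" and CRF V3.0, but the SAP reference list (section 17) cites Protocol V3.0 of 17 Jan 2020 and CRF V2.0. SAP 2.1 declares the analysis consistent with the protocol and lists no departure. SAP 2.2 says that this is the first SAP version.

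**The concern.** A trial should have one planned sample size. SAP 1.2 places the final analysis after Part B is complete, and the planned number decides when that is. No formal calculation supports either figure, so the stated number is the only planned stopping point for enrolment.

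If the trial closes at 60, it is one third short by the protocol (30/90 = 33%). If it closes at 90, it is half as large again as the SAP allows (30/60 = 50%). Either outcome could later be questioned as a choice made after seeing data, and the documents would offer no defence.

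The conflict also reaches the allocation list, because SAP 3.3 derives 30 assignments per arm, and it changes the precision of the Part B primary comparison on worst itching NRS.

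**Working it through.** **1. The figures side by side**

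| Part B | Protocol | SAP |
|---|---|---|
| Enrolled | 90 (synopsis, 5.1) | 60 (3.1) |
| To complete | 90 (10.1) | 60 (3.2) |
| Per arm | 45:45 (synopsis) | 30:30 (3.1, 3.3) |
| Screened | about 100 (synopsis) | about 66 (3.1) |
| Screened / enrolled | 100/90 = 1.11 | 66/60 = 1.10 |

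Each column adds up: 45 + 45 = 90 and 30 + 30 = 60, with nearly the same screening allowance. The conflict is between the documents.

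**2. Can the two numbers be reconciled?**

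- *Enrolled versus completed.* No. Each document uses its own number for both.
- *Attrition.* Going from 90 to 60 needs a loss of 30/90 = 33%. Neither document mentions such a rate.
- *Replacement of withdrawals.* The protocol synopsis and section 6.4 allow extra patients if more safety and tolerability data are needed. They give no number, and the rule does not change the planned total.
- *A recorded change.* None appears in SAP section 2 or elsewhere in the text.

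Neither 60 nor 90 can be reproduced from inputs, because the documents give no effect size, SD, power or dropout rate.

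**3. Effect on precision, with no SD needed**

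For a two-group comparison with n per arm, SE = SD × √(2/n).

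- SE ratio, 30 versus 45 per arm: √(45/30) = 1.22.
- 95% CI width ratio: [t(0.975, 58) × √(2/30)] / [t(0.975, 88) × √(2/45)] = 0.517 / 0.419 = 1.23.

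**4. Illustration in NRS points**

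The documents give no SD, so 2.0 to 3.0 points is an assumption. Half-width = t(0.975, 2n − 2) × SD × √(2/n). The difference detectable with 80% power comes from the noncentral t at two-sided 5%, the level given in SAP 10.2. It is 0.736 SD at 30 per arm and 0.597 SD at 45.

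| Assumed SD | CI half-width, 60 patients | CI half-width, 90 patients | Detectable, 60 patients | Detectable, 90 patients |
|---|---|---|---|---|
| 2.0 | 1.03 | 0.84 | 1.47 | 1.19 |
| 2.5 | 1.29 | 1.05 | 1.84 | 1.49 |
| 3.0 | 1.55 | 1.26 | 2.21 | 1.79 |

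These are simple two-group figures without dropout. The planned MMRM adjusts for baseline itch and prior anti-itch medication and may be more precise; dropout would work the other way.

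**The case against.** The strongest reply is that this is a version lag. The SAP may have copied 60 faithfully from the protocol version it was written against, with the protocol changed later. A first SAP could not explain a change not yet made, and the version of the protocol text to hand cannot be seen. This is plausible and may well be the cause, but the text cannot confirm it: the SAP names two protocol versions, and neither citation shows which number that version carried. Even if true, the SAP would need updating.

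Second, the protocol delegates statistical analysis to the SAP, not enrolment, so a number restated in the SAP cannot change the target. That is a fair argument for the protocol having precedence. It does not settle which protocol version is current.

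Third, the planned number enters no estimator, analysis set or model. The FAS is whoever was randomised and dosed, the MMRM is the same at either size, and no power claim fails because none is made. All of this is correct. The harm lies in the undefined end of enrolment and in the precision, not in the analysis method.

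Fourth, the consistency statement in SAP 2.1 speaks of the statistical analysis and may not strictly cover sample size. That stands, and the conflict does not depend on it.

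**Conclusion.** The conflict is real and unresolved in the text: 90 against 60 patients, or 45 against 30 per arm. Nothing in the documents reconciles the two, and neither is shown to be the wrong one. The loss of precision at the smaller size is a factor of 1.22 in the standard error and 1.23 in interval width, assuming only equal SD and equal completeness. The values in NRS points rest on assumed SDs and show scale only. Because the number fixes when Part B ends and how many assignments are made, it should be settled before Part B is unblinded.

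**What to change.** - State the Part B number and arm sizes in force.
- Make SAP 3.1, 3.2 and 3.3 agree with the protocol synopsis, 5.1 and 10.1. If 90 is in force, revise the SAP; if 60 is in force, amend the protocol.
- Confirm that the Part B randomisation list, which is not part of either document, has the matching length.
- Cite one protocol version and one CRF version in SAP 1.1 and section 17.
- Record the change and its reason in SAP section 2, so that 2.1 either holds for the sample size as well or lists the departure.

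If 90 is in force, the cost is a text revision of the SAP and the list check. If 60 is in force, add a protocol amendment and its review. No patients beyond the number already planned are needed.

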3.3 Randomisation, blinding and unblinding procedures

Subjects will be randomized into the study once they have completed screening and the Day -1 pre-dosing assessments and have satisfied all eligibility criteria.

Hemodialysis subjects with moderate-to-severe pruritus will be assigned random allocation number as the following ratio in each study part.

For Part A, patients will be randomized into a 2:1 ratio to receive LT5001 drug product or placebo. Thus, LT5001 group, the resulting allocated subjects will be 12 subjects. The placebo group will contain 6 subjects.

For Part B, patients will be randomized into a 1:1 ratio to receive LT5001 drug product or placebo. Thus, LT5001 group, the resulting allocated subjects will be 30 subjects. The placebo group will contain 30 subjects.

QMS Document Name: Statistical Analysis Plan	Page 9 of 33
QMS No (include version ref): STF-015-GL.02	Document date: 09JUL2019
CONFIDENTIAL	

The CRO will maintain the randomization code in a secure location with controls to prevent unauthorized access, including the computer program written to generate the randomization, randomization codes, program log, seed number used by the program, copy of the randomization plan along with approval documentation as appropriate, and the write protected electronic storage medium.

The site and CRO will name an unblinded statistician to provide the randomization code. Investigators, pharmacists, site staff, patients, CRO, and the Sponsor will remain blinded to individual patients' treatment assignment for the duration of the study until the study unblinding has been authorized.

In order to preserve the blind, study drug will be prepared and administered in a manner that masks the content for both the patient and staff member administering the drug.

4 Analysis Sets

Enrolled Population (ENR)

The enrolled population will include all patients who provided informed consent. Summary of screening failures and randomized patients will be displayed for ENR population.

Safety Analysis Set (SAS)

The SAS will include all patients who receive at least 1 dose of LT5001 drug product or placebo in Parts A and B. Patients will be analyzed according to the treatment they actually received.

The Safety Population will be used for all safety analysis (adverse events, clinical laboratory tests, vital signs, physical examinations and application site examination).

Full Analysis Set (FAS)

The Full Analysis Set will include all randomized patients who received at least 1 dose of LT5001 drug product or placebo. Subjects will be analyzed based on the treatment assigned.

The Full Analysis Set will be used for all efficacy analysis and demographics.

Per Protocol Set (PP)

The per-protocol population will comprise all FAS patients who complete the study procedures without a major protocol deviation that would impact on efficacy and high compliance.

The PP population will also be used for the analysis of efficacy.

The Per Protocol Set is defined as patients who:

- Receive at least 80% of the planned study drug doses
- Did not receive a different treatment than the treatment to which they were randomized
- Had a mean baseline Worst Itching Intensity score > 4.0
- Had a non-missing weekly mean of daily 24-hour Worst Itching NRS score available for at least 75% of study weeks (weeks with >3 missing daily values set to missing)
- Did not receive prohibited medication listed in protocol section 7.7.3

QMS Document Name: Statistical Analysis Plan	Page 10 of 33
QMS No (include version ref): STF-015-GL.02	Document date: 09JUL2019
CONFIDENTIAL	

- Did not have other major protocol violations that would impact efficacy outcomes

The assignment of subjects to the different analysis set will be done prior to unblinding during a blind data review meeting. All subjects excluded from the different analysis sets will be listed together with the reason for exclusion.

Pharmacokinetic analysis set (PKAS)

The PKAS will include patients who have received at least 1 dose of LT5001 drug product and have at least 1 measured concentration of LT5001 drug product at a scheduled PK time point after dosing.

Subjects will be analyzed based on the actual treatment received.

The Pharmacokinetic analysis set will be used for all PK analysis of part A.

5 General Statistical Methods and Definitions

5.1 General statistical methods

The statistical analyses will be presented by treatment group for the different analysis sets as defined in section 4 Analysis Sets.

Statistical Consideration

Continuous variables will be summarized using descriptive statistics (Number of subjects, Mean, Standard deviation (SD), Median, Min, Max).

Categorical variables will be summarized with descriptive statistics (number of subjects, frequency counts, and percentage of subjects).

Changes from baseline in categorical data will be summarized using shift tables where appropriate.

Unless otherwise stated, the calculation of proportions will be based on the number of available data and missing data will not be presented separately.

Common Calculations

- 1 week = 7 days
- 1 year = 365.25 days

Duration is calculated as :

- Duration (days) = (End Date – Start Date + 1)
- Duration (weeks) = (End Date – Start Date + 1) / 7
- Duration (months) = (End Date – Start Date + 1) / 30.44
- Duration (years) = (End Date – Start Date + 1) / 365.25

Multicenter Studies

- Part A: 1 site in Taiwan

QMS Document Name: Statistical Analysis Plan	Page 11 of 33
QMS No (include version ref): STF-015-GL.02	Document date: 09JUL2019
CONFIDENTIAL	

- Part B: 4 sites in Taiwan

This study will be conducted by multiple investigators at various centres in part B.

Data from all centres will be pooled prior to analysis in part B. No data adjustment will be made for multicentre analysis.

Output Presentations

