7.3 Method of Assigning Patients to Treatment Groups

The CROs will prepare the randomization scheme in accordance with its SOPs and the randomization plan, which reflect GCP standards. Refer to [Section 10.3](#) for a description of

randomization methods. Eligible patients will be assigned to a treatment group according to the list of patient randomization assignments.

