8.6.2 Questionnaire interviewed by investigator or designee

The Skindex-10 Scale and 5-D Itch scale are both multidimensional scales not only access pruritus intensity but measure the impact of pruritus on patients. The Skindex-10 evaluate how the patient's itch affects three important domains of quality of life including 3 domains (disease, mood/emotional distress, and social functioning) as noted in [Appendix B](#). Subjects filled one of seven bubbles ("0 [never bothered], 1, 2, 3, 4, 5, and 6 [always bothered]") for each of the questions. The total score was the sum of the numeric value of each answered question ranging from 0 to 60, with higher scores indicating worse itch-related quality of life. The 5-D itch scale include 5 domains (the duration, degree, direction, disability, and distribution) as noted in [Appendix C](#), with a total score ranging from 5 (no itching) to 25 (maximum severity).

The Skindex-10 and 5-D Itch scale will be performed when patients were in the dialysis unit. The investigator or designee will conduct a face-to-face interview to assist the subject complete the Skindex-10 Scale and 5-D Itch scale. Before the interview, the investigator or designee will be trained by the medical monitor to ensure the accuracy and maintain the consistency of the interview across individuals. Subjects will complete the questionnaire without input on the answers from the study team.

The questionnaire interview will be conducted every 2 weeks at day 1 (Visit 1), day 15 (Visit 5), and day 29 (Visit 7) in Part A, and day 1 (Visit 1), day 15 (Visit 3), day 29 (Visit 5), day 43 (Visit 7), day 57 (Visit 9) in Part B as noted in the schedule of assessments ([Table 2.1](#), [Table 2.2](#)).

In practice, the order of the procedures is recommended as follows but may be adjusted upon investigator's judgement: (1) Before dialysis: vital signs, blood sampling for the PK and

laboratory tests (2) During dialysis: Skindex-10 Scale and 5-D Itch scale (3) After dialysis: body weight, physical examination, and other safety assessment procedures.

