10.3 Randomization

Patients will be randomized into the study once they have completed screening and the Day -1 predosing assessments and have satisfied all eligibility criteria.

For Part A, patients will be randomized into a 2:1 ratio to receive LT5001 drug product or placebo. For Part B, patients will be randomized into a 1:1 ratio to receive LT5001 drug product or placebo.

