5.5 Covariates and Strata

In Mixed-effect model repeated measures analysis, baseline itch and prior anti-itch medication use will be considered as covariates for efficacy endpoints in Part B.

Strata is not applicable in this study.

6 Subject Accounting and Disposition

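### Part B has four sites, but site is neither a described stratification factor nor a model term: a modest, avoidable loss of precision, not a bias

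*SAP*

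**What the plan says.** SAP 5.1, under its multicentre heading, gives one site for Part A and, for the efficacy part, "Part B: 4 sites in Taiwan". It then states: "Data from all centres will be pooled prior to analysis in part B. No data adjustment will be made for multicentre analysis". SAP 5.5 names baseline itch and prior anti-itch medication as covariates and adds: "Strata is not applicable in this study". The model code in SAP 10.1 contains treatment, time, their interaction, baseline itch and prior medication, and nothing for site.

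On allocation, Protocol 10.3 says: "For Part B, patients will be randomized into a 1:1 ratio to receive LT5001 drug product or placebo". SAP 3.3 repeats the ratio. Neither section names a block size or a stratification factor. Protocol 7.3 places the detail elsewhere: "The CROs will prepare the randomization scheme in accordance with its SOPs and the randomization plan". That plan is not part of the public documents.

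**The concern.** Site can plausibly matter here. Local staff instruct patients on applying the ointment (Protocol 7.2). Background antipruritics follow the patient's own physician (Protocol 7.7.1). For the two quality-of-life scales, Protocol 8.6.2 says: "The investigator or designee will conduct a face-to-face interview to assist the subject complete the Skindex-10 Scale and 5-D Itch scale".

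If outcomes differ between sites and the arms are unevenly split within sites, the difference between arms carries some site noise. That noise can be kept out at allocation, by blocking within site, or removed in part afterwards, by fitting site. The documents describe the first nowhere and exclude the second, without giving a reason. Protocol 10.1 and SAP 3.2 both say that no formal sample size calculation was done, so there is no documented power margin to absorb noise that could be avoided.

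**Working it through.** The plan gives no power or precision figure to reproduce, so the question is how much precision site costs.

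**Inputs from the documents.** Four sites (SAP 5.1); 1:1 allocation (Protocol 10.3); two-sided 5% test (SAP 10.2); Part B size 60 (SAP 3.2) or 90 (Protocol 10.1). The two sizes conflict and need reconciling separately; both are carried here.

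**Assumptions.** Equal sites, total SD 2.0 NRS points, true difference 1.0, no dropout, and a between-site share of variance (ICC) of 0 to 0.20. The documents give none of these. One time point is used, without the two covariates, so the ICC is best read as what remains after them.

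**Step 1: stratify and fit site, against doing neither.** Take the total variance as 1, with m patients per site.
- Unstratified and unadjusted, the variance is proportional to (1 − ICC) + k·ICC, with k = 3m/(N − 1). For N = 60, k = 45/59 = 0.763.
- Stratified and adjusted, it is proportional to 1 − ICC.
- Ratios at N = 60:
  - ICC 0.05: 0.95/0.988 = 0.96
  - ICC 0.10: 0.90/0.976 = 0.92
  - ICC 0.15: 0.85/0.964 = 0.88
- The square roots are 0.98, 0.96 and 0.94, so the standard error falls by about 2%, 4% and 6%.
- N = 90 gives the same ratios to two decimals. Simulation of allocations in study-wide blocks of 4 also gave 0.96, 0.92 and 0.88.

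**Step 2: fit site without stratifying.** Chance imbalance within sites inflates the adjusted variance by about (N − 1)/(N − 4).
- N = 60: 59/56 = 1.054. Ratios become 1.01, 0.97 and 0.93: no gain at ICC 0.05, and about 3% and 7% at 0.10 and 0.15.
- N = 90: 89/86 = 1.035. Ratios are about 1.00, 0.95 and 0.91.

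**Step 3: is there bias or a false-positive problem?** In 6,000 simulated trials per setting with unstratified allocation, the unadjusted estimate averaged within about 0.015 of the truth, and type I error lay between 0.046 and 0.055. In a single trial the chance shift due to site at N = 60 has SD √(4·k·ICC·2.0²/60) = 0.10, 0.14 and 0.20 NRS points at ICC 0.05, 0.10 and 0.20. The total standard error is about 2.0·√(2/30) = 0.52. The shift is already contained in that standard error.

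**Step 4: what if the list is blocked by site?** At ICC 0.20 and N = 60 the true variance is proportional to 0.80, but the unadjusted model estimates about 0.80 + 0.763·0.20 = 0.953. The standard error is too large by √(0.953/0.80) = 1.09. The effective critical value becomes 2.00 × 1.09 = 2.18 on 58 degrees of freedom, a two-sided level of about 0.033. Simulation gave 0.034.

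**Step 5: power by simulation** (SD 2.0, difference 1.0):

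| N | ICC | Neither | Fit site only | Stratify and fit |
|---|---|---|---|---|
| 60 | 0 | 0.47 | 0.46 | 0.46 |
| 60 | 0.05 | 0.48 | 0.47 | 0.49 |
| 60 | 0.10 | 0.48 | 0.49 | 0.52 |
| 60 | 0.20 | 0.49 | 0.52 | 0.56 |
| 90 | 0.20 | 0.67 | 0.72 | 0.75 |

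Simulation error on each entry is about √(0.25/6000) = 0.006, so differences of 0.01 are not meaningful.

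**The case against.** The strongest reply is that pooling four sites in one country, in a Phase 2 part without a formal sample size, is prespecified and valid, and that the gain is small and rests on an ICC nobody has stated. Most of that stands. It limits the size of the point but does not remove it, because the remedy is cheap.

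Four stronger readings are tempting, and the documents do not support them.

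- **That imbalance within sites biases the treatment difference.** It does not: the error averages to zero and the unadjusted standard error covers it (Step 3).
- **That allocation is known to be unstratified by site.** This is an inference. Protocol 10.3 and SAP 3.3 are silent, and the sentence in SAP 5.5 sits beside the analysis covariates, so it may concern analysis strata only. The randomization plan could block by site. The site term would still be warranted, for the reason in Step 4.
- **That a badly lopsided site is likely.** At N = 60 the simulated chance that some site ends at 2:1 or worse is about 58%, but only when every site has exactly 15 patients, where a 10:5 split counts. Strictly worse than 2:1 it is about 23%; with sites of 16, 16, 14 and 14 it is about 38%. Nor does counting lopsided sites measure error in the estimate.
- **That the plan does nothing about site differences.** Baseline itch and prior anti-itch medication are in the model, which takes up much of any prescribing difference, and antipruritic regimens must stay unchanged (Protocol 7.7.1). Interviewers are trained for consistency (Protocol 8.6.2). The primary NRS is a patient diary, so interviewer effects bear only on 5-D Itch and Skindex-10.

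**Conclusion.** The point holds as one of efficiency and clear specification. Site is absent from the described allocation and excluded from the analysis, and no reason is given. If allocation is unstratified, the analysis is valid but less precise than it could be: about 4% to 12% in variance at assumed ICCs of 0.05 to 0.15. In power, stratifying and fitting site is worth about 1 to 7 points at N = 60 for ICCs of 0.05 to 0.20, and about 8 points at N = 90 and 0.20. If sites do not differ, nothing is gained. If allocation is blocked by site, the planned test is conservative and the SAP's statement on strata would need correcting. All sizes depend on the assumed ICC, SD, effect and equal sites; the direction does not, provided sites differ at all. Stratification is the main part of the gain.

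**What to change.** **Before Part B opens.** In Protocol 10.3 and SAP 3.3, randomise Part B 1:1 in permuted blocks within site, with block size concealed or varied. In SAP 5.1 replace "No data adjustment will be made for multicentre analysis", and in SAP 5.5 replace "Strata is not applicable in this study", with a statement that site is the stratification factor and enters the Part B NRS, 5-D Itch and Skindex-10 models as a fixed effect. Add site to the model code in SAP 10.1. Keep the analysis without site as a sensitivity analysis.

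**If the list already exists.** State in SAP 3.3 how it was built. If it is blocked by site, fit site as above. If it is fixed and unstratified, say so and prespecify the site-adjusted model as a sensitivity analysis.

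**Cost.** A site-wise list and one model term (4 − 1 = 3 degrees of freedom), with no extra patients, visits or staff. If sites do not differ, the loss is negligible. Blocking within small sites makes allocation slightly easier to predict, which is why block size should be concealed or varied.
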